4. PARTICIPANT SELECTION

4.1. Eligibility Criteria

Participants must meet the following criteria on screening examination to be eligible to participate in the study:

- 4.1.1. Participants must have histologically or cytologically confirmed breast cancer that is metastatic (Stage IV) or unresectable and for which standard curative or palliative measures do not exist or are no longer effective (i.e. patients have progressed on their most recent anticancer therapy).
- 4.1.2. Participants must have measurable disease by Response Evaluation Criteria In Solid Tumors (RECIST). (See Section 11 for the definition of measurable disease.)
- 4.1.3. All immunohistochemical subtypes of breast cancer (Estrogen receptor +/-, progesterone receptor +/-, and HER2+/-) are eligible. HER2 positive breast cancer (HER2 3+ by immunohistochemistry or amplification by FISH > 2) must have progressed on prior standard HER2 therapy or have a contraindication to anti-HER2 therapy.
- 4.1.4. Participants must have at least 1 prior chemotherapy regimen for metastatic disease, with no limit on total number of lines of prior therapy. EXPANSION COHORT ONLY: Participants may have any number of prior chemotherapy regimens for metastatic disease, with no limit on total number of lines of prior therapy. This also includes participants with no prior chemotherapy for metastatic disease.
- 4.1.5. Age \geq 18 years
- 4.1.6. Life expectancy \geq 12 weeks.
- 4.1.7. ECOG performance status ≤ 2 (see Appendix A)
- 4.1.8. Participants must have normal organ and marrow function as defined below:
 - Leukocytes $\geq 3,000/\text{mm}^3$
 - Absolute neutrophil count $\geq 1,500/\text{mm}^3$
 - Platelets $\geq 100,000/\text{mm}^3$

- total bilirubin \leq 1.5X the upper limit of institutional normal limits(subjects with Gilbert's Syndrome may have a bilirubin \geq 1.5 X the upper limit of institutional normal limit if no evidence of biliary obstruction exists)
- AST (SGOT)/ALT (SGPT) \leq 2.5 X institutional upper limit of normal (or \leq 5 X institutional upper limit of normal if significant liver involvement of tumor is present)
- creatinine \leq 2mg/dL or creatinine clearance \geq 50 mL/min/1.73 m² for subjects with creatinine levels above institutional normal.

- 4.1.9. Archived tissue block or 25 unstained slides (from primary and/or metastatic tumor) if available for correlative exploratory studies. Absence of available tissue will not exclude subjects from participating.
- 4.1.10. CNS metastases are allowed if they are clinically stable without current evidence of symptomatic progression and do not require steroids (except for patients who recently completed brain radiation and are on stable or tapering doses of steroids), whole brain radiation therapy, or stereotactic radiosurgery (gamma/cyber knife). This may include brain metastases not previously treated or previously treated if they are clinically stable as described above. Note: CNS metastases in a location that the treating physician believes to be at high risk for causing symptoms in the very near future are encouraged to receive treatment first. Patients receiving brain radiation may start treatment 1 week after completing radiation and such patients may continue steroids.
- 4.1.11. The effects of ABT-888 on the developing human fetus are unknown. For this reason, women of child-bearing potential and men must agree to use adequate contraception (hormonal or barrier method of birth control; abstinence) prior to study entry and for the duration of study participation. Should a woman become pregnant or suspect she is pregnant while participating in this study, she should inform her treating physician immediately.
- 4.1.12. Women of childbearing potential must have a negative pregnancy test within 14 days of registration.
- 4.1.13. Ability to understand and the willingness to sign a written IRB approved informed consent document.
- 4.1.14. Patients enrolled in the expansion cohort must have confirmed BRCA1 or BRCA2 status with a pre-existing genetic report from a laboratory certified to carry out clinical genetic testing. Patients must have a BRCA1/2 mutation known to cause loss of gene function (clinical deleterious or suspected deleterious mutation).

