6.4. Duration of Therapy

Duration of therapy will depend on individual response, evidence of disease progression and tolerance. In the absence of treatment delays due to adverse events, treatment may continue indefinitely or until one of the following criteria applies:

- Disease progression (note: see Section 6.6 for CNS-only progression),
- Intercurrent illness that prevents further administration of treatment,
- Unacceptable adverse event(s),
- Participant decides to withdraw from the study,
- General or specific changes in the participant's condition render the participant unacceptable for further treatment in the opinion of the treating investigator, or
- Study drug becomes unavailable due to manufacturer or other causes.

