6.5. Duration of Follow Up

Participants will be followed for two years after removal from study. . Participants removed from study for unacceptable adverse events will be followed until resolution or stabilization of the adverse event. Patients will be followed off study by their primary treating physician. At the time of informed consent, patients will be asked for permission to contact the patient or their family in the future after coming off therapy to determine patient outcome or if any relevant follow up issues arise from the clinical or exploratory endpoints.

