12. ADVERSE EVENT REPORTING REQUIREMENTS

12.1. General

Adverse event collection and reporting is a routine part of every clinical trial. This study will use the descriptions and grading scales found in the NCI Common Terminology Criteria for Adverse Events version 3.0 (CTCAE v3.0) that is available at <http://ctep.cancer.gov/reporting//ctc.html>.

Information on all adverse events, whether reported by the participant, directly observed, or detected by physical examination, laboratory test or other means, will be collected, recorded, followed and reported as described in the following sections.

Adverse events experienced by participants will be collected and reported from initiation of study medication, throughout the study, and within 30 days of the last dose of study medication. Participants who experience an ongoing adverse event or related to a study procedures and/or study medication beyond 30 days will continue to be contacted by a member of the study team until the event is resolved, stabilized, or determined to be irreversible by the participating investigator.

Participants should be instructed to report any serious post-study event(s) that might reasonably be related to participation in this study. The investigator should notify the IRB and any other applicable regulatory agency of any unanticipated death or adverse event occurring after a participant has discontinued or terminated study participation that may reasonably be related to the study.

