12.5. Manufacturer Notification by Investigator

12.5.1. Serious Adverse Event Reporting Requirements

All events meeting the criteria for Serious Adverse Event (see Section 12.2) that occur after the initial dose of study treatment, during treatment, or within 30 days of the last dose of treatment must be reported as serious adverse events.

The participating investigator must report each serious adverse event, regardless attribution, to the Principal Investigator within 24 hours of learning of the occurrence. In the event that the participating investigator does not become aware of the serious adverse event immediately (e.g., participant sought treatment elsewhere), the participating investigator is to report the event within 24 hours after learning of it and document the time of his or her first awareness of the adverse event. Report serious adverse events by telephone and facsimile on the Medwatch 3500A form to:

Oncology Group Safety Desk
Abbott Laboratories
[name]
[name]
[name]

Office: [contact]
[contact] (toll-free North America only) or
[contact]
e-mail: [contact]

Within the following 24-48 hours, the participating investigator must provide follow-up information on the serious adverse event. Follow-up information should describe whether the event has resolved or continues, if and how the event was treated, and whether the participant will continue or discontinue study participation.

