15.2. Sample Size/Accrual Rate

A total of 41 patients who receive at least one cycle of study drug will be enrolled.

Subjects who discontinue study participation after enrollment but before receiving one cycle of study drug will be replaced with an additional subject. Subjects who receive at least one cycle of study drugs but who never have follow-up tumor measurements done will be counted as non-responders.

Approximately 2-3 patients per month, minimally, are expected to accrue over 18 months for a total of 41 subjects. However, due to investigator and patient interest, accrual may be rapid between all DFHCC sites.

In the expansion cohort a total of approximately 20 patients are planned to be enrolled, with up to 22 allowed, in case of possible rapid accrual over a short period of time. This will allow patients who may have signed consent prior to formal administrative closure of the trial to enroll. Approximately 5 patients per month are expected to accrue over 4 months.

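### Section 4.1.11 ties contraception and pregnancy reporting to undefined study participation rather than to the last dose, so it guarantees no post-dose period

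*Combined protocol and SAP*

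**What the plan says.** Section 4.1.11 asks men, and women who could become pregnant, to use "adequate contraception (hormonal or barrier method of birth control; abstinence) prior to study entry and for the duration of study participation". The only reason it gives is that the fetal effects of ABT-888 are unknown; TMZ is not named. Its reporting instruction begins "Should a woman become pregnant or suspect she is pregnant while participating in this study" and sends the woman to her treating physician.

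The protocol uses the term *study participation* in other places without defining it. Section 12.1 speaks of events "occurring after a participant has discontinued or terminated study participation". Section 12.5.1 asks investigators to state "whether the participant will continue or discontinue study participation". Section 15.2 provides that "Subjects who discontinue study participation after enrollment but before receiving one cycle of study drug will be replaced with an additional subject".

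On leaving the trial, 6.4 lists "Participant decides to withdraw from the study" among the reasons to stop, and 6.6 removes a patient from study once any 6.4 reason applies. Section 6.5 then says "Participants will be followed for two years after removal from study" and "Patients will be followed off study by their primary treating physician".

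On hazard, 4.2.11 recognises teratogenic or abortifacient potential for both drugs. Section 8.2.2 describes TMZ as potentially mutagenic, in the setting of handling precautions.

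**The concern.** A contraception rule for drugs with recognised reproductive hazard should state how long after the last dose it runs. This one ends at a point that the protocol never fixes. Two patients with the same exposure could be protected for very different periods, depending on when and why they leave and on how their physician reads the term. A patient who withdraws partway through a dosing week could, on one reading, stop contraception that day.

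The reporting sentence has the same weakness. A pregnancy recognised shortly after removal may fall outside the instruction that the patient was given.

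The stake is participant and fetal safety. No endpoint, sample size or analysis depends on it.

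**Working it through.** The plan gives no figure to reproduce. The check sets out the possible end points and counts days from the last dose for each.

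**Inputs**
- Cycle length: 28 days, taken from start to start (2.1, Table 6.1).
- Last ABT-888 dose on day 7, last TMZ dose on day 5 (Table 6.1).
- Scheduling window: ±3 days (Section 10).
- Restaging scan: 0-14 days before each odd-numbered cycle (Table 10.1, footnote k).
- Toxicity delay: up to 3 weeks, or 21 days (7.2).
- Adverse event collection: to 30 days after the last dose (12.1).
- Follow-up: two years after removal (6.5).

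**Reading 1: participation ends at removal**

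The next odd cycle starts on day 29 ± 3, that is day 26 to 32 of the even cycle. The scan falls 0-14 days earlier:
- earliest: 26 − 14 = day 12
- latest: 32 − 0 = day 32

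If the patient is removed on the scan day with no dose delay:
- ABT-888: 12 − 7 = 5 to 32 − 7 = 25 days after the last dose
- TMZ: 12 − 5 = 7 to 32 − 5 = 27 days after the last dose

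If removal waits for the planned next-cycle visit (day 26 to 32):
- ABT-888: 26 − 7 = 19 to 32 − 7 = 25 days
- TMZ: 26 − 5 = 21 to 32 − 5 = 27 days

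If the scan is pushed back by a full 21-day toxicity delay:
- ABT-888: 5 + 21 = 26 to 25 + 21 = 46 days
- TMZ: 7 + 21 = 28 to 27 + 21 = 48 days

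If the patient withdraws on a dosing day: about 0 days.

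**Reading 2: participation ends at the Off Study visit**

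Table 10.1 schedules this visit, with examination, imaging and adverse event review, and Section 7 refers to a final study visit. Neither dates it from the last dose, so no number follows.

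**Reading 3: participation runs through the adverse event window**

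About 30 days after the last dose.

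**Reading 4: participation includes follow-up**

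Two years after removal.

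Across the four readings, the period after the last dose runs from about 0 days to about two years. The text of 4.1.11 selects none of them.

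**Clearance.** Using five half-lives as a conventional yardstick (an assumption), ABT-888 takes 5 × 4 to 5 × 5 = 20-25 hours (half-life from 8.1.2) and TMZ takes 5 × 1.8 = 9 hours (8.2.1). Both drugs are gone within about a day.

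**Added duty under a 30-day floor, counted from the later last dose (ABT-888, day 7)**

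| Reading of the present rule | Extra days of contraception |
|---|---|
| Removal at a no-delay scan | 30 − 25 = 5 to 30 − 5 = 25 |
| Withdrawal on a dosing day | up to 30 − 0 = 30 |
| 30-day window | about 0 |
| Two-year follow-up | none; the duty would become shorter unless the label or brochure sets a long period |

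**The case against.** The strongest reply is that removal need not be the end of participation. Section 12.1 first covers adverse events to 30 days after the last dose, then continued contact for ongoing events, and only then turns to events after participation has ended. That order fits a 30-day reading at least as well. The protocol also distinguishes being off treatment from being off study, schedules an Off Study assessment, and still calls people in follow-up participants. This stands. A reader might infer that the duty plainly ends at removal, but the documents do not establish that, and every day count under Reading 1 depends on it. The 5-25 and 7-27 day figures also assume removal on the scan day itself. The reply does not supply an end point, however. It adds to the list of possible ones.

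Second, both drugs clear within about a day, and the mutagenicity remark is a handling precaution. The only evidence here of a lasting reproductive effect is the rat combination study in 3.2.1, where testis findings had not recovered after 28 days. That is not a human threshold, it concerns men only, and the documents do not say how many men take part. This also stands: it would go too far to conclude that a specific longer risk period has been shown. Clearance still leaves no stated margin for a patient who withdraws on a dosing day.

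Third, a reader might infer that pregnancies after removal go unreported. Section 12 gives partial cover. Section 12.1 asks participants to report serious, possibly related events after the study, 12.2.2 counts a congenital anomaly or birth defect as serious, and 12.5.1 requires serious events to be reported to 30 days after the last dose. Pregnancy itself is not on the list of serious events, so the cover is incomplete.

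Finally, the trial runs within one cancer center with central registration, so wide differences between sites are less likely than in a dispersed multicenter trial. The removed consent pages, the TMZ label or the Investigator's Brochure may already give a period.

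**Conclusion.** The point holds in limited form. Section 4.1.11 sets both duties by an undefined term that is not counted from the last dose, so the text guarantees no post-dose period for drugs whose reproductive hazard the protocol itself recognises. Depending on the reading, the duty ends anywhere from about 0 days after the last dose to about two years after removal.

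The documents do not support saying that protection always stops at removal, that 30 days is the right length, or that men need a particular longer period. The 30 days in the fix is a floor taken from the protocol's adverse event window, not a derived risk threshold. The rat testis finding is only a reason to check the period for men.

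The reach is mainly the 20-22 expansion-cohort patients (15.2), and among them only men and women who could become pregnant. The 41 primary-cohort patients were already enrolled (3.3), although 15.1 mentions one still on study. Endpoints and analyses are untouched.

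This is a cheap safety improvement of minor to moderate priority. Confidence is medium, because the consent pages, label and brochure could not be read.

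**What to change.** In 4.1.11, replace the closing reference to study participation with: *during treatment and for at least 30 days after the last dose of ABT-888 or TMZ, whichever is later, or longer if the TMZ label or Investigator's Brochure requires it (set separately for women and men)*. Apply the same period to the pregnancy-report sentence. Name TMZ beside ABT-888 in the stated reason. Bring the consent form into line if it does not already say this, and tell patients still on treatment.

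The cost is two revised sentences, a small addition to the stated reason, and matching consent text. At the 30-day floor, patients carry at most about 30 more days of contraception; a longer period would apply only if the label or brochure requires one. No visit, procedure or analysis changes.

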4.2. Exclusion Criteria

Participants who exhibit any of the following conditions at screening will not be eligible for admission into the study, with exceptions as noted.

- 4.2.1. Participants who have had chemotherapy, biologic therapy, small molecule targeted therapy or radiotherapy within 14 days prior to entering the study or those who have not recovered from adverse events due to agents administered more than 2 weeks earlier. Anti-cancer hormonal therapy must be stopped 24 hours prior to starting study treatment.
- 4.2.2. Participants may not be receiving any other investigational agents.
- 4.2.3. Prior therapy with TMZ is allowed except if participant has a history of allergic reactions attributed to TMZ, or if therapy was discontinued due to intolerance of or toxicity from TMZ.
- 4.2.4. Prior therapy with an investigational or approved single agent PARP inhibitor is allowed except if participant has a history of allergic reactions attributed to the compound or, if therapy was discontinued due to intolerance of or toxicity from the PARP inhibitor. Prior combination therapy with a PARP inhibitor and chemotherapy is not allowed. EXPANSION COHORT ONLY: Prior therapy with an investigational or approved PARP inhibitor (alone or with combination therapy) is allowed except if participant has a history of allergic reactions attributed to the compound or, if therapy was discontinued due to intolerance of or toxicity from the PARP inhibitor.
- 4.2.5. Leptomeningeal disease. EXPANSION COHORT ONLY: Leptomeningeal disease may be permitted with approval of the study chair for patients who meet the following criteria: a) ECOG PS=0 or 1; b) "clinically stable" leptomeningeal disease defined by no progressive symptoms for the past 30 days and no concurrent use of steroids for the treatment of leptomeningeal disease; and c) standard non-CNS RECIST measurable disease is present.
- 4.2.6. CNS involvement requiring steroids (except for patients who recently completed brain radiation and are on stable or tapering doses of steroids).
- 4.2.7. Uncontrolled intercurrent illness including, but not limited to ongoing or active infection, symptomatic congestive heart failure, unstable angina pectoris, recent myocardial infarction, cardiac arrhythmia, or psychiatric illness/social situations that would limit compliance with study requirements, or other comorbid condition the investigator believes may compromise participant's safe and effective participation in the trial.
- 4.2.8. Inability to comply with requirements of the trial.
- 4.2.9. Concurrent radiation therapy is not permitted while on study
- 4.2.10. Concurrent anti-cancer therapy (hormonal therapy, chemotherapy, biologic therapy, targeted therapy) is not permitted on trial.
- 4.2.11. Pregnant women are excluded from this study because ABT-888 and TMZ are chemotherapy agents with the potential for teratogenic or abortifacient effects. Because there is an unknown but potential risk of adverse events in nursing infants secondary to treatment of the mother, breastfeeding should be discontinued if the mother is treated with ABT-888 or TMZ.
- 4.2.12. History of uncontrolled seizure disorder

4.2.13. Individuals with a history of other malignancies are eligible if they meet the following criteria:

- The other malignancy was treated with curative intent and is deemed by the investigator to be at low risk for recurrence, AND
- A metastatic lesion has been histologically confirmed as breast cancer, AND
- Patient has at least 1 RECIST measurable lesion thought to be breast cancer.
- Individuals with the following cancers are eligible if diagnosed and treated: cervical cancer *in situ*, and basal cell or squamous cell carcinoma of the skin.

4.3. Inclusion of Women, Minorities and Other Underrepresented Populations

This study is open to women and men. This study is open to participants of all ethnic and cultural groups. No specific recruitment efforts are planned for traditionally underrepresented populations.

5. REGISTRATION PROCEDURES

5.1. General Guidelines for DF/HCC and DF/PCC Institutions

Institutions will register eligible participants with the DF/HCC Quality Assurance Office for Clinical Trials (QACT) central registration system. Registration must occur prior to the initiation of therapy. Any participant not registered to the protocol before treatment begins will be considered ineligible and registration will be denied.

A member of the study team will confirm eligibility criteria and complete the protocol-specific eligibility checklist.

Following registration, participants may begin protocol treatment. Issues that would cause treatment delays should be discussed with the Principal Investigator. If a participant does not receive protocol therapy following registration, the participant's protocol status must be changed. Notify the QACT Registrar of participant status changes as soon as possible.

5.2. Registration Process for DF/HCC and DF/PCC Institutions

The QACT registration staff is accessible on Monday through Friday, from 8:00 AM to 5:00 PM Eastern Standard Time. In emergency situations when a participant must begin treatment during off-hours or holidays, call the QACT registration line at [contact] and follow the instructions for registering participants after hours.

The registration procedures are as follows:

1. Obtain written informed consent from the participant prior to the performance of any study related procedures or assessments.
2. Complete the protocol-specific eligibility checklist using the eligibility assessment documented in the participant's medical/research record. **To be eligible for registration to the study, the participant must meet each inclusion and exclusion criteria listed on the eligibility checklist.**

Reminder: Confirm eligibility for ancillary studies at the same time as eligibility for the treatment study. Registration to both treatment and ancillary studies will not be completed if eligibility requirements are not met for all studies.

3. Fax the eligibility checklist(s) and all pages of the consent form(s) to the QACT at [contact].

Exception: DF/PCC Affiliate sites must fax the entire signed consent form including HIPAA Privacy Authorization and the eligibility checklist to the Network Affiliate Office. The Network Affiliate Office will register the participant with the QACT.

4. The QACT Registrar will (a) validate eligibility, (b) register the participant on the study, and (c) randomize the participant when applicable.
5. The QACT Registrar will send an email confirmation of the registration and/or randomization to the person initiating the registration immediately following the registration and/or randomization.

